5.5 Blinding of Study

As a pilot study to assess feasibility, all subjects will receive PAE. Therefore, neither the study physicians nor patients will be blinded to the treatment protocol.

5.6 Receiving, Storage, Dispensing and Return

5.6.1 Receipt of Investigational Device Supplies

LC Bead LUMI will be stored within the Vascular and Interventional Radiology procedural suite.

5.6.2 Storage

LC Bead LUMI must be stored in a cool, dark, dry place in their original packing.

5.6.3 Dispensing

LC Bead LUMI are routinely used in VIR. No study specific dispensing techniques will be used.

5.6.4 Return or Destruction of Investigational Device

The Institution and Sponsor-Investigator shall, return any such Product to Company promptly if requested by the Company upon the completion or termination of the Study for which such Product was being utilized, or promptly dispose of or destroy, as the Company may reasonably direct, all of its remaining stocks of Product. Risk of loss to any such Product shall reside with the Institution. Institution shall reimburse Company for any loss of or damage to any Product provided by Company under this Agreement due to the negligence of Institution or Sponsor-Investigator, ordinary wear and tear excepted. The Institution and Sponsor-Investigator shall not use any Product provided by Company under this Agreement for any purpose whatsoever except as is necessary for the conduct of the Study.

6.0 Study Procedures

6.1 Pre-Study Visit

Possible enrollees will have already undergone a standard TURP/OP work-up, which typically includes a history, physical exam, urine flow rate recording (Qmax), post-void residual urine volume assessment (PVR), and imaging to measure prostate size. These workups also generally include the following laboratory testing-- UA, PSA, CBC, INR, and chemistry.

6.2 Visit 1 (Vascular Interventional Radiology Clinic)

If a patient qualifies to be a subject in the study based on the inclusion and exclusion criteria listed in section 4.3 and 4.4, the study coordinator will be notified. The coordinator will review the study with the patient and obtain written informed consent. Once the subject is enrolled in the study, he will be seen by one of the co-investigators in either UNC or VIV IR clinic. The procedure will be again described to the patient and any questions will be answered. International Prostate Symptoms Survey (IPSS), International Index of Erectile Function (IIEF) and Quality of Life (QOL) questionnaires will be completed if not done during the pre-study work-up. A CT of the pelvis without contrast will be ordered and obtained prior to visit 2 for baseline evaluation of the prostate unless the patient has one from the prior 6 months. If the patient had a CT of the pelvis within the past 6 months, this CT will be used.

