4.0 Subject Selection and Withdrawal

4.1 General Characteristics of the Proposed Subject Population

Study subjects will be men with moderate severe LUTS refractory to medication with measured prostate gland size >50 grams.

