4.3 Inclusion Criteria

1. Male
2. Age > 40
3. Prostate gland >50 grams as measured by pre-procedural CT
4. Have previously taken BPH medication for 6 months without desired improvement of LUTS or has started medication and stopped due to unwanted side effects
5. Moderate to severe LUTS as defined by IPSS score >18
6. Peak urine flow rate (Qmax) <12 ml/sec
7. Capable of giving informed consent
8. Life expectancy greater than 1 year

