5.0 Study Treatment or Diagnostic Product Procedures

5.1 Description

Subjects will be advised to stop taking their BPH medications two weeks prior to PAE. Though this is advised, it is not required if they cannot tolerate cessation. They will be given a dose of antibiotics on the day of the procedure and continue with oral antibiotics for seven days after the procedure. Additionally, non-steroidal anti-inflammatory medication will be administered mid-procedure. The patients will be given the choice of receiving intravenous anxiolytic and analgesic medication during procedure or proceeding with local anesthetic only.

Ultrasound-guided access into common femoral artery or radial artery will be obtained. An intra-arterial sheath will be placed. Through this sheath a diagnostic catheter will be used to perform pelvic angiography. Based on these images and CT angiography obtained before the procedure, a microcatheter will be fluoroscopically guided into the prostatic artery. LC Bead LUMI will then be injected under fluoroscopic guidance to prevent reflux and non-target embolization. Injection will continue until there is stasis. The catheter will then be guided into the contralateral prostatic artery and repeat embolization will be performed until stasis. If necessary, extraprostatic arterial anastomoses will be embolized with a coil or a gel-foam pledget to protect against non-target embolization. The catheter and sheath will then be removed and hemostasis will be achieved with compression or an intra-arterial closure device. The subject subsequently will be discharged home the same day or the following day.

It is anticipated that less than 4 milliliters of LC Bead LUMI will be required for bilateral embolization. LC Bead LUMI currently have FDA approval for embolization of hypervascular tumors and arterio-venous malformations.

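### The single pre-PAE IPSS can be both qualifying score and baseline, has no age limit and can precede the advised drug stop, so the 6-month change can include regression to the mean and a change in drug status

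*Combined protocol and SAP*

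**What the plan says.** The primary endpoint is the reduction in IPSS at 6 months (3.2). Section 4.3 makes the same instrument an entry criterion: "Moderate to severe LUTS as defined by IPSS score >18". Section 6.2 opens with "If a patient qualifies to be a subject in the study based on the inclusion and exclusion criteria", so eligibility is settled before the Visit 1 activities that follow. At Visit 1 the IPSS, IIEF and QoL "questionnaires will be completed if not done during the pre-study work-up". For imaging, the same section sets a window: "If the patient had a CT of the pelvis within the past 6 months, this CT will be used". It sets none for a reused IPSS. The Time and Events table marks IPSS at Visit 1 and at 3, 6 and 12 months, and leaves Visit 2 blank.

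On medication, Section 5.1 says "Subjects will be advised to stop taking their BPH medications two weeks prior to PAE", and adds: "Though this is advised, it is not required if they cannot tolerate cessation". Section 6.3 places PAE within 4 weeks of Visit 1. Section 5.4 asks men to discontinue BPH drugs after PAE, allows some to stay on them, and keeps doses stable unless there is a medical need. Section 5.3 asks when drugs were stopped before the procedure.

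Section 8.2 calculates percent change from the baseline without saying which score or drug status that means. Every subject receives PAE (5.2).

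**The concern.** Men are admitted because their score lies above a cut-off. If that score is also the baseline, part of any later fall is expected without any treatment effect, because scores that passed the cut-off partly through a transient high tend to be lower when repeated. A separate baseline score or a control group would show or remove this. The plan requires neither.

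Drug status raises a second problem. A man scored on medication and followed up off it has two things changed: the procedure and the drug. If stopping the drug worsens symptoms, his measured improvement is too small for an off-drug comparison.

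At stake is the estimate of 6-month change. Section 2.0 gives preliminary estimates of such changes as the study's purpose, and Section 8.1 intends the study to supply sample size data for a larger trial. A pre-PAE score that was not collected cannot be recovered after treatment.

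**Working it through.** **Is one pre-PAE score enough under the plan?** Section 6.1 does not list IPSS in the usual work-up, and the table marks it only at Visit 1. Yet 6.2 needs eligibility, and so a score above 18, before the Visit 1 questionnaires. These places do not fit together neatly, but either reading leaves one required score before PAE and none at Visit 2. (The 6.8 flow chart is not shown.)

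**Can it precede the drug stop?** Visit 1 may be up to 4 weeks before PAE and the stop is advised 2 weeks before. A Visit 1 score can therefore come up to 4 − 2 = 2 weeks before the stop. A reused work-up score can be older without limit.

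**The plan's own figure.** Section 8.1 states 3.60% precision for percent change in IPSS with n = 20. The SD and confidence level behind it are not in the documents, so it can only be solved backwards. As a 95% half-width it implies an SD of 3.60 × √20 / 1.96 = 8.21 percentage points, or 7.69 with the t quantile on 19 degrees of freedom. Neither can be confirmed. The figure serves below only as a yardstick.

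**Regression to the mean.** All inputs are assumptions: mean of recorded scores before selection 16 to 22, SD 6 to 7, and correlation ρ between repeat scores 0.7 to 0.9. The cut is 18.5, since scores are whole numbers above 18. With a = (18.5 − mean)/SD, and no treatment effect:

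- mean baseline among those admitted = mean + SD × φ(a)/(1 − Φ(a))
- expected fall = (1 − ρ) × SD × φ(a)/(1 − Φ(a))

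| Case | Mean, SD, ρ | a | φ(a)/(1 − Φ(a)) | Mean baseline | Expected fall |
|---|---|---|---|---|---|
| Low | 22, 6, 0.9 | −0.583 | 0.467 | 24.8 | 0.1 × 6 × 0.467 = 0.28 points (1.1%) |
| Middle | 20, 6, 0.8 | −0.250 | 0.646 | 23.9 | 0.2 × 6 × 0.646 = 0.78 points (3.2%) |
| High | 16, 7, 0.7 | 0.357 | 1.038 | 23.3 | 0.3 × 7 × 1.038 = 2.18 points (9.4%) |

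The range is about 0.3 to 2.2 points. The middle case lies just inside the stated 3.60%; the high case lies outside it.

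**With a separate second score as baseline.** A simulation with whole-number scores bounded at 0 and 35 (mean 18 to 24, SD 6, ρ 0.7 to 0.9) gave a fall of 0.20 to 1.55 points from the qualifying score and at most 0.01 from a separate score. That assumes all pairs of scores correlate equally. If the correlation of the qualifying score with follow-up is 0.05 to 0.10 lower than with the second score, about 0.1 to 0.7 points remain.

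**Drug status.** Let a share p of men be on drug at baseline, all men be off drug at follow-up, and stopping add d points. The mean change is then understated by p × d against an off-drug comparison. Neither p nor d is in the documents. With the middle case and p = 0.5, d = 1 gives a net 0.78 − 0.5 = +0.28 points (overstated), and d = 3 gives 0.78 − 1.5 = −0.72 points (understated). The sign turns on unknown inputs.

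**The case against.** This is a declared open-label, single-arm, descriptive pilot. It tests no hypothesis, so no test is invalidated, and no baseline schedule could attribute the change to PAE. That stands.

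Reuse of an old score may be uncommon. IPSS is not in the usual work-up list, and a score taken at Visit 1 is at most 4 weeks old at PAE. That also stands, but it does not answer the dual use of one score or its timing against the drug stop.

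The drug-status effect does not reach everyone. Section 4.3 admits a man who "has started medication and stopped due to unwanted side effects", and 5.1 and 5.4 let others stay on treatment. The population is described as having "LUTS refractory to medication", so on drug before versus off drug after PAE may be exactly the comparison wanted. In that case the drug change belongs to the contrast and only regression to the mean remains. The plan does not say which is meant. Section 5.3 captures the stop time, and the case report form, which is not among the documents, may capture more.

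A reader might infer that the results could not be interpreted at all. That goes too far: with only one score required, there is little doubt which it is, and only its date and drug status are open. A reader might also infer that the benefit must be exaggerated. The documents do not support that, because the two effects can oppose each other.

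**Conclusion.** The point holds as a limited one. Followed as written, the plan lets one score of unlimited age serve as both qualifier and baseline, and lets it precede the advised drug stop, with no control arm to show the consequences. The 6-month change can therefore include regression to the mean and, for some men, a change in drug status. Their net size and direction cannot be derived from the documents.

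The 0.3 to 2.2 points for regression to the mean rest wholly on assumed means, SDs and correlations. They are an illustration, not an estimate for this trial, and do not show that the stated precision is exceeded. The case for acting is that the primary estimate is affected and the remedy is cheap.

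**What to change.** 1. First state which contrast is intended: baseline on drug or off drug, each against off-drug follow-up.
2. Collect a second IPSS and QoL before PAE, separate from the qualifying score, and use it as the baseline for change and for clinical success. Take it at Visit 2 just before PAE if an off-drug baseline is intended, or at Visit 1 before the advised stop if an on-drug baseline is intended.
3. Keep the qualifying score for eligibility and as a sensitivity baseline.
4. Set an age limit for any reused work-up IPSS, as 6.2 already does for CT.
5. Record the date and BPH drug status with each IPSS, building on the stop time already asked for in 5.3.
6. Report the 6-month change overall and, descriptively, by drug status.

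The cost is a few minutes of patient time at an existing visit, two data fields and one table with very small subgroups. The repeat score reduces but does not remove either effect: some men will not stop their drugs, and some regression to the mean may remain. It cannot attribute the change to PAE.

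No drug rule is proposed. As a separate matter, 4.3 and 5.4 contradict each other on prior medical therapy and must be reconciled.

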6.3 Visit 2 (PAE)

PAE will be performed as described in part 5.1 above within 4 weeks of Visit 1. The day following the procedure, the subject will be contacted by telephone to inquire about symptoms that could be the result of the procedure. In addition, they will be given a pager number to reach a physician 24 hours a day to report any adverse symptoms and receive medical advice.

6.4 Visit 3 (1 Day Follow Up)

Subjects will be contacted by study personnel the day after PAE to inquire about delayed onset complications.

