3.3 Secondary Study Endpoints

1. Improvement of QoL score at 6 months
2. Improvement of uroflowmetry (Qmax, PVR) at 6 months
3. Reduction of prostate volume at 6 months
4. Percentage of prostate infarcted at 6 months
5. Incidence of non-target embolization at 6 months
6. Incidence of minor complications at 6 months
7. Improvement in IIEF at 6 months

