5.3 Subject Compliance Monitoring

Study coordinators and physicians will inquire of the subjects to determine when they have stopped taking their BPH medications prior to the procedure. Additionally, the subjects will be asked if they completed all seven days of their post-procedural antibiotic regimen.

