6.5 Visit 4 (3 Month Follow-Up)

Subjects will return 90 +/- 7 days after PAE to complete IPSS, IIEF, and QOL questionnaires; to have Qmax and PVR measured; and to have a follow up CT of the pelvis to evaluate for non-target embolization and PV changes as well as percent prostate infarction.

[figure not shown]

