9.0 Risk Analysis

9.1 Anticipated Risks

A recent meta-analysis of PAE data from 662 patients in nine studies reported only two major complication (0.3% major complication rate) involving bladder ischemia requiring surgery and severe urinary sepsis requiring hospitalization. Among minor complications transient rectalgia and/or dysuria (9.1%), acute urinary retention (7.9%) and transient hematuria (4.4%) were the most common (1).

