9.3 Recording of Adverse Events

Research subjects will be questioned about adverse effects by telephone the day following the procedure. In addition they will be given a pager number to reach a physician 24 hours a day to report adverse effects and receive medical advice. The subjects will also be questioned about possible adverse effects at each follow-up visit.

All observed or volunteered adverse effects (serious or non-serious) and abnormal test findings, regardless of treatment group, if applicable, or suspected causal relationship to the investigational device or, if applicable, other study treatment or diagnostic product(s) will be recorded in the subjects' case histories. For all adverse effects, sufficient information will be pursued and/or obtained so as to permit 1) an adequate determination of the outcome of the effect (i.e., whether the effect should be classified as a *serious adverse effect*) and; 2) an assessment of the casual relationship between the adverse effect and the investigational device or, if applicable, the other study treatment or diagnostic product(s).

Adverse effects or abnormal test findings felt to be associated with the investigational device or, if applicable, other study treatment or diagnostic product(s) will be followed until the effect (or its sequelae) or the abnormal test finding resolves or stabilizes at a level acceptable to the investigator-sponsor.

An abnormal test finding will be classified as an *adverse effect* if one or more of the following criteria are met:

- The test finding is accompanied by clinical symptoms

- The test finding necessitates additional diagnostic evaluation(s) or medical/surgical intervention; including significant additional concomitant drug treatment or other therapy
 - Note: simply repeating a test finding, in the absence of any of the other listed criteria, does not constitute an adverse effect.
- The test finding leads to a change in study protocol or discontinuation of subject participation in the clinical research study
- The test finding is considered an adverse effect by the Sponsor-Investigator.

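### Between the day-1 call and the 3-month visit no contact is scheduled, so minor complications that start and resolve in that gap depend on volunteered reports or later recall and may be undercounted

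*Combined protocol and SAP*

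**What the plan says.** After several hours of observation following the procedure (7.1), the early safety contact is a telephone call on day 1. Section 6.4 describes it thus: "Subjects will be contacted by study personnel the day after PAE to inquire about delayed onset complications". The next scheduled contact is in 6.5: "Subjects will return 90 +/- 7 days after PAE". Visits at 180 and 360 days follow (6.6, 6.7). Section 9.3 adds active questioning at those visits: "The subjects will also be questioned about possible adverse effects at each follow-up visit".

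Between contacts, reporting is left to the subject. Under 6.3, "they will be given a pager number to reach a physician 24 hours a day to report any adverse symptoms and receive medical advice". Section 7.1 adds a nurse telephone line, and 9.3 records adverse effects whether observed or volunteered.

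The time-and-events table (Figure 1, section 16.0) shows nothing between the procedure and the 3-month visit, omits the day-1 call and has no adverse-event row. The flow chart under 6.8 does not appear in the text available for this review.

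The endpoints concerned are 3.3 item 6, "Incidence of minor complications at 6 months", and the secondary safety endpoint in 3.5, which is limited to device-related minor complications and requires Clavien-Dindo classification.

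Section 9.1 gives the expected events: rectalgia and/or dysuria at 9.1%, described as transient, and then "acute urinary retention (7.9%) and transient hematuria (4.4%) were the most common". Section 5.3 adds a compliance item without a date: "the subjects will be asked if they completed all seven days of their post-procedural antibiotic regimen".

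**The concern.** The one early call is meant to find delayed complications, yet it comes on day 1 and no second early contact follows. Mild symptoms that appear in the first weeks and settle on their own are the least likely to prompt a call to a physician or nurse, and the hardest to recall and grade some three months later.

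The study has one arm, so no control group shares the same incomplete collection. Any shortfall passes directly into the reported rate, and it makes the device look safer. Section 1.5 says there are no published data on this device in prostatic artery embolization, and 3.1 names initial safety as a purpose of the study. The rate would probably be used in planning the larger trial.

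The antibiotic question in 5.3 shows the same gap. The seven-day course ends after the day-1 call, so the first scheduled contact at which completion can be asked about is month 3.

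**Working it through.** The plan states no figure for completeness of adverse-event collection, so there is none to reproduce.

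**Length of the gap.** From 6.4 and 6.5:
- Earliest: 83 - 1 = 82 days
- Nominal: 90 - 1 = 89 days
- Latest: 97 - 1 = 96 days

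**Could anything else fill it?** The reviews every two months in 9.7.1 and 11.1.5 examine case report forms and source documents; they are not described as subject contacts. The safety monitor's reviews after treatment of subjects 1, 5, 10 and 20 may, for the newest subject, see only day-1 or volunteered data.

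**Expected events.** Count = 20 x rate, with 20 subjects from 4.2 and rates from 9.1:
- Rectalgia and/or dysuria (called transient): 20 x 0.091 = 1.82
- Acute urinary retention (not called transient): 20 x 0.079 = 1.58
- Hematuria (called transient): 20 x 0.044 = 0.88
- All three: 20 x 0.214 = 4.28
- The two called transient: 20 x 0.135 = 2.70

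These are events, not necessarily distinct men.

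**Illustrative loss.** Assume that 30-50% of the transient events are missed and that urinary retention is fully captured. The documents support neither figure; they give no onset times and no capture rates.
- Lost: 2.70 x 0.30 = 0.81, to 2.70 x 0.50 = 1.35
- Recorded: 4.28 - 0.81 = 3.47, to 4.28 - 1.35 = 2.93
- Events per 20 men: 3.47/20 = 17%, to 2.93/20 = 15%, against 21.4% with full capture

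This treats every transient event as starting after day 1. Each one present at observation or at the day-1 call reduces the loss.

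**Chance of recording no event of a given kind.** P = (1 - rate x capture)^20, at full and at an assumed 50% capture:
- Rectalgia/dysuria: (1 - 0.091)^20 = 15%, rising to (1 - 0.0455)^20 = 39%
- Hematuria: (1 - 0.044)^20 = 41%, rising to (1 - 0.022)^20 = 64%

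One missed case moves a rate by 1/20 = 5 percentage points.

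**The case against.** The protocol does provide real-time reporting during the gap. The physician pager runs around the clock for the stated purpose of reporting symptoms, the nurse line is a second route, and volunteered effects are recorded. Events on the day of the procedure or by the next day are covered by observation and the call. All of this stands. It means recall is the fallback only for later events that were not volunteered. It does not close the gap, because both routes depend on the man deciding to report.

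A reader might go further and infer that transient complications are collected only by recall and will certainly be undercounted. The documents do not support that, given the reporting routes and the absence of onset times or capture rates. A reader might also apply a 30-50% loss to all 4.28 events, giving 4.28 x 0.50 = 2.1 to 4.28 x 0.70 = 3.0 recorded. That is not supported either: 9.1 does not call urinary retention transient, and retention would plausibly prompt a call (an inference).

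Three further points have weight:
- The rates in 9.1 cover minor complications after the procedure in a meta-analysis of nine studies, whereas 3.5 counts only device-related ones with this device. The illustration does not separate them.
- Section 2.0 does not list minor complications among the parameters to be estimated. With 20 men, precision is poor in any case: the exact 95% interval is about 6-44% for 4/20 and about 3-38% for 3/20, so a loss of about one event is small against that width. But the interval does not correct a one-directional error.
- The antibiotic question is a compliance item, not an endpoint, and could be asked at month 3.

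Nothing here shows that major complications, which drive 3.4 and the stopping rule in 9.6, would be missed.

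**Conclusion.** The concern holds as a risk of under-ascertainment. For 82 to 96 days after the day-1 call, a minor complication that starts and resolves is captured only if it is volunteered or later recalled. The likely direction of error in 3.3 item 6 and 3.5 is downward.

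The size is unknown. Under the stated assumptions it is about one event in 20 men (0.8 to 1.4), and less if some events start by day 1. The schedule and the direction of risk rest on the documents; the amount rests on the assumed 30-50% loss and on full capture of retention. This is a weakness worth correcting at low cost. It does not invalidate the study, and certain or wholesale undercounting has not been shown.

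**What to change.** Add structured telephone adverse-event contacts by the existing coordinator in the early weeks, for example one shortly after day 7 and one near day 30. The exact timing is a matter of judgement; the first would also give the antibiotic question in 5.3 a scheduled contact. Use one standard set of adverse-event questions on day 1 and at these calls; the documents show no such set at present.

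Add the contacts to section 6, and the contacts and an adverse-event row to Figure 1. At the same time reconcile the visit labels: section 6 calls the day-1 contact Visit 3 and the 3-month visit Visit 4, while Figure 1 labels the 3-month visit Visit 3.

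This is data collection only and changes no care. The cost is 2 x 20 = 40 short calls and a protocol amendment. The reported minor-complication rate will probably be higher.
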